4.2 Randomization and Blinding

A total of 44 randomized blocks are needed for the study. For random assignment and sequencing purposes, each randomized block consists of five integers that correspond to the four treatment and one control group assignment. The VA Pittsburgh Investigational Drug Service (IDS) Pharmacist will randomly determine which integer corresponds to the control group and the integers corresponding to the

four treatment groups; this random assignment will only be done once, and the same integers will correspond to the assigned groups across all blocks. The Investigational Drug Service Pharmacist will use a randomizer function available on www.random.org. In order to maintain the blind, the control and treatment group assignments will not be divulged to any study staff other than the anesthesia care team member who prepares the nerve block injections. The sequence of treatment/control assignments within each of the randomized blocks will be determined by the VA Pittsburgh StatCore using the sequence generator at website random.org. Each block will have a separate sequence generated for it.

The randomization scheme will be prepared before the start of the trial. Sequentially numbered and sealed envelopes containing the randomized control or treatment group assignment will be provided by the Investigational Drug Service (IDS) Pharmacist. The IDS Pharmacist will retain the sealed envelopes and will be responsible for providing them to the PI or designee as requested prior to the scheduled procedure. The PI or designee will then provide the sealed envelope to the nerve block drug mixer. The IDS Pharmacist will coordinate the provision of the nerve block drugs. The drugs will be stored in an automated dispensing cabinet and accessible only to the designated nerve block mixers.

After a subject has been enrolled, the study coordinator will submit a Treatment Allocation Request form to the IDS Pharmacist.

- 1) The Treatment Allocation Form will indicate the subject's criteria:
 - a) Age: ≤ 69 or > 69 years
 - b) Type of procedure: total knee replacement or total hip replacement
 - c) Diabetes status: present or absent
- 2) Based on the criteria noted on the Treatment Allocation Request form, the IDS Pharmacist will provide the next available treatment assignment envelope.
- 3) The IDS Pharmacist will also provide the mixer with a form to document the details of the nerve block drugs mixed, e.g., date and time of preparation, preparer's name, and drugs utilized.

Prior to the procedure, the mixer will open the sealed envelope to determine the treatment assignment. The mixer will prepare the assigned nerve block as per the established preparation guidelines and complete the accompanying documentation form. The re-sealed treatment assignment envelope and documentation form will ultimately be returned to the IDS Pharmacist, to prevent any inadvertent un-blinding of the treatment assignment.

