2.0 Background and Significance

2.1 Background

The surgical invasiveness of elective total knee/hip arthroplasty (TKA/THA) in veterans provides a logical model under controlled conditions for evaluating physical therapy / occupational therapy (PT/OT) effectiveness after major lower extremity polytrauma sustained in the battlefield. The central idea of this protocol (in the grant application submitted to the Department of Defense) is to measure pain (primary) and rehabilitation (exploratory) outcomes after TKA/THA as influenced by factors under the direction of the anesthesiologist physician, specifically nerve block drug selection (plain bupivacaine versus the described 4-drug mixture as single-injection nerve blocks).

For these TKA/THA cases, our standard of care regional anesthesia (RegA) technique entails spinal anesthesia to ensure adequate anesthesia and excellent surgical conditions during surgery. Spinal anesthesia alone does not provide any sustained pain relief after surgery. As a result, our institutional standard of care for TKA/THA also entails single-injection nerve blocks (with the described 4-drug combination) of both L2-L4 and L4-S3 nerves/plexi, placed before surgery. Applying these nerve blocks before surgery ensures that our patients do not have significant pain after the spinal anesthetic “wears off” later in the day after surgery.

Nerve blocks can be administered as single-injections or via percutaneous indwelling catheters, the latter of which being far more labor-intensive and expensive.(1) We do not use indwelling perineural catheters at our institution. In the absence of the described 4-drug **MultiModal PeriNeural Analgesia** (MMPNA), the plain bupivacaine single-injection (0.1% - 0.25%) nerve block is typically reported as having 8-16 hr analgesic duration. In our institutional standard of care experience, the addition of clonidine-buprenorphine-dexamethasone (CBD) to bupivacaine 0.1% – 0.25% yields an average duration of analgesia of approximately 36 hr. We are unable to determine if this additional analgesic duration inhibits physical therapy after surgery (one of our exploratory aims for this specific study).

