4.0 Research Design and Methods

4.1 Type of Study

This is a single-site study that will take place at VA Pittsburgh Healthcare System, Pittsburgh, PA. It is a prospective randomized clinical trial evaluating the two different nerve block injection drugs for TKA and THA, introduced above and described further below. All described RegA techniques strategically avoid GETA and high-dose opioids, and the immediate postoperative complications (from GETA and high-dose opioids) that inhibit full-capacity cognitive function needed to accomplish PT/OT goals during the first 2 days after TKA/THA. Two hundred (200) total patients will be recruited and evaluated for study outcomes pre-TKA/THA (100 for TKA, 100 for THA). Following pre-surgical evaluation, patients will be block-randomized (stratified by [a] TKA vs. THA surgical procedure, [b] age, and [c] presence of diabetes). After surgery, all patients will undergo the same standardized PT/OT best-evidence care plans consistent with current clinical care at our institution. Evaluation of study outcomes will take place during the first two days after surgery, throughout the remainder of the hospital stay (which typically ranges from 2 to 5 days, including discharge day), and during the first two orthopedic post-op follow-up evaluations. The primary outcome is pain at 24 hr after surgery, and exploratory outcomes include physical therapy progress and anesthesia-related symptoms. We will also assess additional metrics of anesthesia and physical therapy success such as range of motion, physical function and performance testing, length of hospital stay, discharge placement, readmission, falls, and other adverse events.

Study Treatment Groups:

Institutional Standard of Care (ISOC)

All patients will receive a standardized bupivacaine spinal anesthetic, consistent with current institutional practice. All patients will receive pre-medications for the prevention of pain, nausea, vomiting, and gastroesophageal reflux, consistent with current institutional practice. All patients will receive intravenous hydration, intravenous antiemetics, and intravenous blood pressure support (e.g., intravenous phenylephrine bolus/infusion) consistent with our current institutional practice. The need for intraoperative blood transfusion will occur based on current institutional practice and collaborative decision-making between the surgical and anesthesia teams, consistent with current institutional practice.

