ISOC MMPNA Block Group (n=80 TKA and 80 THA patients) will receive the ISOC 4-drug MMPNA nerve blocks at the L2-L4 and L4-S3 nerves/plexi. These blocks will be placed before the administration of spinal anesthesia, per our ISOC.

Active Control Block Group (n=20 TKA and 20 THA patients) will receive “active control” nerve blocks comprised of plain bupivacaine. As with the ISOC MMPNA Block Group, these blocks will be placed before the administration of spinal anesthesia, per our ISOC. Again, these blocks will involve the same L2-L4 and L4-S3 nerves/plexi as those for the ISOC MMPNA Block Group.

All study team members will be blinded to the nerve block treatment group/drug the patient receives/received for the described blocks. The only unblinded person regarding the study treatment will be the anesthesia team member who prepares the nerve block injection syringes, based on the randomization envelope assignment. This person who prepares the drug syringes will be otherwise uninvolved with the care of the study patient.

Table 1. Anatomic location of the analgesic nerve blocks used based on TKA versus THA

Basic description of regional anesthesia and analgesia care plan	TKA block details	THA details
Spinal anesthesia, L2-L4 and L4-S3 perineural/plexus single-injection nerve blocks	L2-L4 nerve block entails the femoral nerve in the groin. The L4-S3 nerve block entails the sciatic nerve as it emerges from the sciatic notch deep to the gluteal musculature.	L2-L4 plexus block entails the lumbar plexus within the psoas compartment, 2-3 inches lateral to the lumbar spine midline. The L4-S3 plexus block entails the lumbosacral trunk and parasacral plexus, which lies lateral to the lateral margin of the proximal sacrum. The plexus lies deep to the sacroiliac ligament.

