6.4 Inclusion/Exclusion Criteria

Inclusion Criteria:

Subjects must meet all of the following inclusion criteria to be eligible for participation in this study.

1. Age between 18 and 85, and undergoing a total knee or hip replacement.
2. Fluent in English, decision competent, willing and able to provide written informed consent, and able to complete the study's schedule of assessments.
3. Able to walk >3m without an assisting device.
4. Have a BMI $\leq 40 \text{ kg/m}^2$.

Exclusion Criteria:

Subjects who meet *any* of the following exclusion criteria will not be enrolled in this study.

1. Current participation in another orthopedic/PT/rehab/anesthesiology interventional clinical trial.
2. Are at significant behavioral risks or have refractory major psychiatric disorders.
3. Revision surgery on the same extremity.
4. Have an ASA Physical Status classification of 4 or higher.
5. Have been diagnosed with clinically significant neuropathy with its origins in either diabetes or other causes; have neuromuscular disease that would influence data collection.
6. Have a surgically-fused lumbar spine, or a spinal cord simulator, or other condition that would contraindicate or prohibit the conduct of spinal anesthesia.
7. At significant risk for postoperative substance abuse, or immediate-postoperative substance abuse withdrawal symptoms (alcohol, cocaine, enrolled in methadone or buprenorphine opioid withdrawal programs, etc.). Previous or current use of marijuana will not be an exclusion for study enrollment.
8. Are undergoing TKA/THA for a tumor.
9. Have contraindications (e.g., anaphylaxis) to any of the study drugs.
10. Have a systemic fungal infection.
11. Have a known hypersensitivity to bupivacaine hydrochloride or to any local anesthetic of the amide-type or to other components of bupivacaine hydrochloride solutions.
12. Have a known or suspected buprenorphine hypersensitivity (not including nausea and/or vomiting).
13. Have a GI obstruction.
14. Have paralytic ileus.
15. Pregnant women
16. Have had a kidney or liver transplant.

Veteran subjects will not be excluded from participation based on smoking status, diagnosis of obstructive sleep apnea, or baseline monitored consumption of therapeutic opioids for documented

medical indications; instead, these variables will be codified and quantified for subsequent covariate statistical analysis. Prior to study enrollment, the principal investigator has the final decision regarding patient eligibility.

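### The protocol prints a fixed block of five with one control, so staff who recognise earlier arms from block wear-off could deduce some later allocations; varying and withholding the block size is a cheap improvement

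*Combined protocol and SAP*

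**What the plan says.** Section 4.1 describes block randomisation stratified by procedure, age and diabetes, with 80 four-drug (MMPNA) and 20 plain-bupivacaine patients per procedure. Section 4.2 gives the block structure: "each randomized block consists of five integers that correspond to the four treatment and one control group assignment". It adds that "A total of 44 randomized blocks are needed for the study". It describes no variation in block size and does not say that the size is kept from study staff. The stratum facts are entered by the study coordinator on the allocation request form, which goes to IDS after enrolment.

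On who decides entry, section 6.4 says that "the principal investigator has the final decision regarding patient eligibility". Section 6.5 instead gives the final determination to one of the physician-investigators.

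On how the arms differ after surgery, section 2.1 says that the plain bupivacaine "nerve block is typically reported as having 8-16 hr analgesic duration", against roughly 36 h for the four-drug block at this site. Section 5.6 plans on 15 h (SD 7.5) against 30 h (SD 15) and cites observed four-drug data of 40 h (SD 14). Block duration is itself measured during the hospital stay (section 4.4).

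**The concern.** Blinded syringes hide the arm at injection, but not necessarily a day or two later. With constant block length and content, and strata that staff can see, a patient's place in the block can be counted. Once one patient in a block is recognised as the control, every later place in that block is four-drug. If the first four look four-drug, the fifth is control.

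A person who can anticipate the next allocation and also influences eligibility or timing could, even unintentionally, admit different kinds of patient to the two arms. Such selection happens before treatment, so blinded outcome assessment does not remove it. The question is how much could realistically be deduced.

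**Working it through.** **1. The plan's own figures.** Per procedure, 100 / 5 = 20 blocks, which gives 20 control and 80 four-drug patients, as section 4.1 states. For 200 patients at least 40 blocks are needed. The stated 44 blocks hold 44 × 5 = 220 places; over 2 × 2 × 2 = 8 strata, 44 / 8 = 5.5, so the number per stratum cannot be equal. Spare blocks for unfinished strata would explain the excess. The plan gives no predictability figure.

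**2. Ceiling: perfect recognition.** The control is equally likely to be in any of five places. A place is certain if the control has already appeared, or if it is the fifth place and no control has appeared.

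| Control at place | Certain places |
|---|---|
| 1 | 4 |
| 2 | 3 |
| 3 | 2 |
| 4 | 1 |
| 5 | 1 |

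The total is 11 of 25 = 44%. Ten of these are four-drug (40%) and one is control (4%). Over 200 allocations that is 88: 80 four-drug and 8 control. Allowing for unfinished last blocks in eight strata (assumed splits), it is about 42%.

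**3. Imperfect recognition from duration.** Assume normal durations. Let L_i be the ratio of the control density to the four-drug density at the duration of earlier patient i in the block. The chance that place p is the control is then 1 / (ΣL_i + 6 − p), summed over i < p. Simulated results:

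| Durations, h (SD) | Known with ≥90% certainty | Known with ≥95% certainty | Best guess correct |
|---|---|---|---|
| 15 (7.5) vs 30 (15), section 5.6 planning | 3% | 0.1% | 80.3% |
| 15 (7.5) vs 40 (14), planning control with observed four-drug | 30% | 7% | 81.4% |

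Always guessing four-drug is right 80% of the time; perfect recognition gives 84%. The reason for the gap is overlap. At the planning inputs, 75% of controls but also 25% of four-drug patients fall below 20 h, so the share of such early wear-offs that are controls is 0.2 × 0.748 / (0.2 × 0.748 + 0.8 × 0.252) = 43%. With 40 (14) h it is 71%. The 44% ceiling is reached only when durations barely overlap, for example an assumed 14 (1) vs 36 (5) h.

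**4. Effect on type I error (assumption needed).** Suppose enrolled patients' expected pain shifts by s SD upward or downward according to whether the guessed chance of control is above or below 20%. The bias is s × D, where D is the mean guess sign in controls minus that in four-drug patients. The standard error at 40 vs 160 is √(1/40 + 1/160) = 0.177. The documents give no value for s; the range shown is 0.1 to 0.25.

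- Planning inputs: D = 0.33, bias/SE = 0.19 to 0.46, type I error 5.4 to 7.5%.
- 15 vs 40 h: D = 0.60, bias/SE = 0.34 to 0.85, type I error 6.3 to 14%.

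**5. After the change.** With sizes 5 and 10 drawn at random (taken as equally likely) and unknown to staff, and recognition still perfect, certain allocations fall from 44% to about 10%. The share with under 5% chance of control falls from 40% to about 28%. Withholding the size matters: a published fixed block of 10 with two controls would still leave 28.9% certain.

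**The case against.** The strongest reply is that the safeguards are substantial: IDS custody, sealed sequential envelopes, a mixer otherwise uninvolved with the patient, and assignments not divulged to staff. Fixed blocks under blinded allocation are conventional. Using them to predict would require counting in each of eight strata, with the earlier result known before the next enrolment in the same stratum. The 22 patients mentioned in Amendment 6 average 22 / 8 = 2.75 per stratum, less than one block. Oral analgesia is meant to supplement the block and delay peak pain (section 5.2), which blurs recognition. Entry also passes through a coordinator and the clinical care team (section 6.5), and the covariate adjustment in section 5.1 would absorb part of any selection on measured prognosis. All of this stands, and it limits the size of the problem. It does not make the block structure less predictable.

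A reader might infer three stronger things that the documents do not support.

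- *That 44% of allocations would be known in practice.* This needs near-perfect recognition, which the section 5.6 durations do not give.
- *That type I error could reach 29%.* That figure needs perfect recognition and a full 0.25 SD shift at every departure from 20%, even 25% against 20% at the second place. If the shift is scaled to the distance from 20%, perfect recognition gives 5.4 to 7.4%.
- *That the courier step exposes the allocation.* Section 4.2 says "The PI or designee will then provide the sealed envelope to the nerve block drug mixer", but the envelope is sealed and requested after enrolment. Carrying it adds nothing to the deduction.

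**Conclusion.** The point holds as a modest weakness in allocation concealment, not as an error in the design. The block structure is printed, constant and countable within known strata, and the arms are expected to separate visibly in hospital. The ceiling is 44% certain allocations. A working range is about 3 to 30% known with at least 90% certainty, depending on whether the four-drug duration is nearer the planned 30 h or the observed 40 h. These figures assume normal durations, one recogniser who tracks every stratum, and earlier outcomes known in time. The type I error figures also rest on an enrolment shift that is assumed, and nothing in the documents suggests that selective enrolment has occurred. Sections 6.4 and 6.5 differ on who finally decides eligibility, but either way the decision lies with investigators who can hold the protocol.

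**What to change.** For blocks not yet opened in each stratum, draw the size at random from 5 (one control) and 10 (two controls). Finish blocks already open as they stand. Remove the fixed-five sentence from section 4.2 and keep the sizes in a document held only by IDS and the randomisation statistician.

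The cost is new sequences for unissued envelopes and one amended paragraph, plus slightly more imbalance in control counts per stratum when a last block is unfinished. The gain is partial. On the rule in step 4, perfect recognition would still give a type I error of about 7.6 to 22%, against 8.7 to 29% now.

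Sending the envelope from IDS straight to the mixer, who already receives a form from IDS, is optional housekeeping and does not address this mechanism.

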4.4 Data Collection

Primary Outcome – Pain

Pain - Pain will be measured by the Short-Form McGill Pain Questionnaire (36). (SF-MPQ, version 2) and the Defense and Veterans Pain Rating Scale (DVPRS, which entails a 0-10 numeric rating scale along with step-function visual cues, color-coded visual cues, and verbal descriptors of pain intensity). The specific aim is the 24-hour pain severity as measured by the SF-MPQ. The DVPRS will be used to assess (i) “rebound pain” for pain with movement, compared with baseline, during and after nerve block analgesic effects are experienced and (ii) “block duration” (11) for time interval between block placement and peak postoperative DVPRS score with movement.

Exploratory Outcomes – Physical Function, Other Symptoms, and Recovery from Anesthesia

Data will be recorded by the research coordinator and/or VAPHS Staff Physical Therapists and/or “without compensation” (WOC) physical therapists hired through the University of Pittsburgh specifically for the care of study patients.

Data Management System

Data management will be coordinated at VAPHS by StatCore. Data entry will be primarily performed using the VA’s REDCap software (https://vhacdweb05.vha.med.va.gov/redcap_v6.0.27/index.php?pid=1440) via laptop or desktop personal computers. Data will never reside on the data collection devices, which serve only as portals to the password protected database. Only authorized members of the study team will have access. Data will reside on the VA Informatics & Computing Infrastructure (VINCI) server – which is also password protected and independent from all other servers. Data will be downloaded from the REDCap server by StatCore for analytic and data management purposes. Downloaded data will reside on a password-protected VAPHS secure shared drive. REDCap is a secure web-based platform that can only be accessed through the VA intranet, and it is situated behind the VA firewall. Account login information is required, and then the data are stored on the REDCap server. The data to be entered (and catalogued in a detailed data dictionary) are password-protected within REDCap via login requirements, and the downloaded data are secured by permission only access to the shared drive (\\\whapthshare\Nerve_Block_Study\).

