The **primary hypothesis** of an improvement in pain (measured by the SF-MPQ- version 2) 24 hr after surgery during in-hospital recovery comparing plain local anesthetics versus ISOC MMPNA will be tested using a mixed model. This procedure will test for nerve block drug treatment and surgical site (hip versus knee) effects, as well as an interaction between them. Differences in pain levels will also be examined across the study's day-of surgery, 1, 2, 3, and 4 day, and Follow-Up Visit 1 and Follow-Up Visit 2 time points. The secondary aims of short- and long-term physical therapy and rehabilitation-related benefits will also be examined for nerve block drug treatment and surgical site by a mixed model. The tertiary aim to determine differences in opioid-related side effects will use a mixed model. As with other analyses, there will be an examination for nerve block drug treatment and surgical site effects, as well as an interaction between them, along with analyses of the other randomization strata (age, diabetes) as described above.

The **exploratory aims** of physical therapy progress, return-to-home benefits, etc. will be examined using a mixed model. This procedure will test for nerve block type and surgical site effects, as well as an interaction between them. Number of days from the joint replacement procedure to the patient's home discharge will be assessed. Pain responses, as measured by the SF-MPQ – version 2, and use of postoperative opioids with additional measurement by the Opioid-Related Symptom Distress Scale will also be assessed. General health status will be evaluated with the SF-8 and SF-36. Measures of pain, analgesic side-effects, and general health status will be covariates included in the modeling of the effect of MMPNA on return-to-home.

Only after all data are analyzed and results are checked and verified by the biostatisticians will the study be unblinded.

5.2 Adverse Events. For adverse events, we will calculate cumulative probability using survival analysis techniques such as the product-limit estimator. Unlike proportions, product-limit estimators can be applied at various times following randomization, and can take into account when adverse events occur. The six-week incidence (and 95% CI) of individual adverse events by organ system and relatedness to the study will be calculated for each group. We will estimate the incidence of adverse

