
5.3 Incidental Findings.

All instances of incidental findings considered to be clinically significant will be addressed in the following manner: the PI will determine whether a finding is significant to warrant further action. If the PI determines the finding is serious enough to be labeled an adverse event; then the issue will be addressed with the patient’s primary care physician or another specialist. If the finding is not a serious event, then it will be listed as ‘incidental’ and no further action will be taken.

NOTE: The study team will capture the study data using CRFs that have been created by the study team. All hard copy documents will be protected and stored using generally-accepted measures for research confidentiality.

5.4 Interim Analysis.

During the course of a clinical trial, there is an ethical mandate to monitor the progress of the trial with interim analyses to ensure patient safety. A number of group sequential methods have been developed which permit comparisons to be made, while maintaining an overall type I error rate. The investigators will work with the Data and Safety Monitoring Board to select an interim monitoring approach. It is likely that an approach which adjusts the type I error rate in a non-uniform fashion, so that the majority of the type I error is conserved for the final treatment comparison. Thus, a large difference would be needed early in the trial to find a significant difference. Statistical significance parameters will be appropriately adjusted to account for these multiple interim analyses. At this time, the interim analyses are projected to occur (separately for TKA and for THA) at 5/20 patients and at 10/40 patients. If at these points the specific aims have been met (for the ISOC MMPNA treatment), then the Data Safety Monitoring Board will be charged with the decision to terminate the study.

5.5 Dissemination of Results.

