11.0 Collaborations

The statistical analysis for this research study will be done in collaboration by VAPHS StatCore. Physical therapy testing at VAPHS will be conducted in conjunction with University of Pittsburgh-hired physical therapists in order to provide study-specific physical therapy coverage on weekends and/or after hours on weekdays.

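### At 4:1 allocation the analyst blind promised in 5.1 cannot hold, and the plan names no one outside StatCore to receive the interim arm labels

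*Combined protocol and SAP*

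**What the plan says.** **Allocation code (4.2).** On the block structure: "each randomized block consists of five integers that correspond to the four treatment and one control group assignment". The pharmacist of the Investigational Drug Service (IDS) decides which integer means control, and "this random assignment will only be done once, and the same integers will correspond to the assigned groups across all blocks". The order of integers comes from elsewhere: "The sequence of treatment/control assignments within each of the randomized blocks will be determined by the VA Pittsburgh StatCore". The scheme is prepared before the trial starts.

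**Roles.** Section 4.4: "Data management will be coordinated at VAPHS by StatCore". Section 11.0: "The statistical analysis for this research study will be done in collaboration by VAPHS StatCore". No other statistical group is named.

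**Blind.** Section 4.1 says that the syringe preparer is the only unblinded person. Section 4.2 says that assignments go to no other study staff. Section 5.1 sets the end of the blind: "Only after all data are analyzed and results are checked and verified by the biostatisticians will the study be unblinded".

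**Comparisons by arm.** Section 5.4: "the interim analyses are projected to occur (separately for TKA and for THA) at 5/20 patients and at 10/40 patients". The DSMB may end the study if the aims are met for MMPNA. The final model in 5.1 tests nerve block type, with planned totals of 40 control and 160 MMPNA patients (4.1).

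**Data decisions left open (5.1).** Values more than 2 SD from the mean are corrected where that can be done and otherwise removed. Transformations or non-parametric methods are used where needed.

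**The concern.** An interim decision that the aims have been met for MMPNA needs the data split by arm, and so does the final model. Someone must therefore hold arm labels well before the moment at which 5.1 says the study is unblinded. With unequal allocation, neutral labels such as A and B do not help, because group size shows which is control.

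This matters because 5.1 leaves real choices to the analyst: which extreme values to correct or remove, whether to transform, and which method to use. No database lock or blind data review is described. If those choices are made with the arms known, they can favour one arm, while the report would still state that analysis came before unblinding.

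The single control integer adds a second layer. StatCore produces the sequences, so the one thing it lacks is which of five integers means control. That one fact applies to every block in the trial.

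**Working it through.** **1. The plan's own counts.** Each block of five holds one control and four MMPNA assignments.
- Per procedure, n = 100: 100 × 1/5 = 20 and 100 × 4/5 = 80. Over two procedures this is 40 and 160, as in 4.1.
- First look: 25/5 = 5 blocks, giving 5 and 20. Second look: 50/5 = 10 blocks, giving 10 and 40. These match 5.4, so its pairs read as control/MMPNA.

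**2. Can masked labels hide the control group?** Assume that each stratum uses its own blocks. Age and diabetes give four strata per procedure, so up to four blocks can be part-used. The control count is highest when each of these has used one slot and that slot is control, which leaves four slots unused in each. The maximum is the whole-number part of (n + 4 × 4)/5.
- n = 25: 41/5 = 8.2, so at most 8 against 17.
- n = 50: 66/5 = 13.2, so at most 13 against 37.
- n = 100: 116/5 = 23.2, so at most 23 against 77.

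Control is the smaller group at every look, even with incomplete blocks.

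**3. How far could one disclosure reach?** Slots prepared: 44 × 5 = 220. Slots beyond the planned 200: 220 − 200 = 20. Used at the first look if both procedures reach it together: 2 × 25 = 50. Planned patients still to come: 220 − 20 − 50 = 150, or 150/200 = 75%. In the limiting case, where one procedure reaches 25 before the other enrols anyone, the figure is 200 − 25 = 175. Two conditions apply: StatCore sees the comparison by arm, and it can link patients to sequence positions. If the control integer were drawn afresh for each block, a look would decode only the blocks it covers.

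**4. Would withholding the code be enough?** Suppose an analyst holds the five integers as equal-sized groups and takes the one with the shortest mean block duration as control. Section 5.6 gives planning values of 15 hr (SD 7.5) for control and 30 hr (SD 15) for MMPNA. With m patients per integer, draw the control mean from N(15, 7.5/√m) and four MMPNA means from N(30, 15/√m). In 200,000 replicates the guess is right with probability 0.92 at m = 5 (25 patients) and 0.99 at m = 10. The documents give no SD for the SF-MPQ. For assumed standardised differences of 0.3 to 1.0, with equal SDs, the probability is 0.39 to 0.84 at m = 5 and 0.76 to 1.00 at m = 40. With no effect it is 0.20, which is chance.

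**The case against.** A reader might infer that the first interim look reveals every past and future allocation to StatCore. The documents do not establish that.
- Section 5.4 does not say who runs the looks. The investigators are to choose the monitoring approach with the DSMB, and 8.0 describes an external DSMB with its own charter, which is not part of these documents. A statistician on the DSMB side would close this route.
- No section says that envelope number, block or integer enters the study database. The allocation request goes from the coordinator to IDS, and the envelope and mixing form return to IDS. Reconstruction from stratum and order of enrolment is plausible but not stated.
- The figure of 220 slots is not a count of future patients: 50 are already used at a joint first look, and 20 exceed the plan.
- An emergency code break reaching StatCore would be speculation, since no such procedure is described.

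A reader might also infer that allocation concealment fails. StatCore is not described as enrolling patients, giving blocks or collecting assessments, so this does not follow. Nor is anyone who gives or collects the patient-reported outcome unblinded by it.

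Two safeguards deserve credit. Section 4.4 provides an audit trail with dates, persons and prior values, and the outlier rule has a numeric threshold. They make changes traceable but do not remove the discretion.

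The best defence of 5.1 is that an analyst could run all five one-against-four contrasts without knowing which integer is control. The plan does not describe this. It would keep the blind only as far as outcomes do not give the code away (step 4), and it could not support a stopping decision without the code.

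These points make the reach across the whole trial conditional. They do not reconcile 5.1 with the comparisons it and 5.4 require.

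**Conclusion.** The concern holds in two parts of different strength.

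**Firm.** The comparison as specified has two arms at 4:1 (5 and 20 at the first look, 40 and 160 at the end). Whoever fits it can identify control, so the order stated in 5.1 cannot hold for that person, whoever runs the interim looks. Sections 4.1, 4.2, 5.1 and 5.4 cannot all be met as written, and the choices in 5.1 on extreme values, transformation and method are still open at that point.

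**Conditional.** If StatCore sees an interim comparison by arm and can link patients to sequence positions, the one control integer would also expose later allocations: up to 150 of 200 planned patients if both procedures reach 25 together. The documents state neither condition.

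The exposure is to blinded data handling and analysis, not to allocation concealment at enrolment. The size of any resulting bias cannot be computed from the documents.

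**What to change.** 1. **Section 5.1.** Replace the sentence on unblinding. Settle all data corrections, exclusions, transformations and the model on data that carry no arm or integer code, lock the database, and only then release the arms for analysis.
2. **Section 5.4.** Have IDS send arm labels, only for the patients in each look, to an analyst on the external DSMB side and not to StatCore. Reconcile 4.1, 4.2, 5.1 and 5.4 on who holds the code and when. Include the IDS pharmacist, who sets the code and whom 4.1 overlooks when it calls the preparer the only unblinded person.
3. **Section 4.2, optional.** Have IDS draw the control integer independently for each wholly unissued block and keep the key. Allocation stays 4:1. This adds protection if step 2 fails but does not replace step 1, because group size still identifies control in any fitted comparison. Leave started blocks alone: the amendment log shows 22 patients already enrolled by Amendment 6.

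Cost: protocol wording, an interim table prepared on the DSMB side, and fresh envelopes for unissued blocks if step 3 is taken. No patients or visits are added.
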